#### 9.1.2 PRIMARY ANALYSIS

Changes from baseline in MADRS will be analyzed using a Mixed Model with Repeated Measures (MMRM). This analysis of covariance mixed-effect model for repeated measures will include treatment (two levels: 1 indicating active treatment and 2 indicating the control), week (5 levels: Weeks 1 through 4 and Week 6), and treatment-by-week interaction as factors, baseline value as a covariate, and subject as a random effect. SAS default covariance structure (variance components) will be assumed. The MMRM with maximum likelihood estimation will utilize the following pseudo- SAS code for analysis:

The primary hypothesis testing will be overall treatment effects. However, for completeness treatment difference at each post baseline week will also be presented. Overall treatment effects, treatment effects at individual post baseline week, and the differences between treatment effects will be estimated using the least-square mean estimates and will be reported together with the 2-sided 95% confidence interval of the treatment differences.

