7.2 Study Entry Criteria

7.2.1 Inclusion Criteria

A subject will be eligible for study participation if the subject meets all of the following criteria:

- 1. Provides written informed consent to participate in the study, is able to understand the procedures and study requirements, and agrees to abide by the study restrictions and return for the required study assessments.
- 2. Male or female outpatients, 18 to 65 years of age, inclusive.
- 3. Currently meets the DSM-5 criteria for MDD without psychotic features, based on the SCID-

5-CT, with a current major depressive episode of at leave 4 weeks in duration at Visit 1.

- 4. MADRS score of ≥ 25 and CGI-S ≥ 4 at Screening (Visit 1) and Baseline (Visit 2).
- 5. Normal physical examination findings and clinical laboratory test results from Screening (Visit 1) or abnormal results that are judged not clinically significant by the investigator.
- 6. Body mass index (BMI) between 18 and 40 kg/m², inclusive.
- 7. If female of childbearing potential, having a negative urine pregnancy test result at Visit 1 and Visit 2, and practicing an adequate method of birth control (e.g. oral or parenteral contraceptives, intrauterine device, double-barrier) and does not plan to become pregnant during the course of the study. Long-term abstinence is acceptable as long as the subject agrees to use double-barrier contraception if they decide to have sexual intercourse. Female subjects using a hormonal contraceptive or intrauterine device must have been doing so for at least 1 month before Screening and must follow that product's package insert instructions including additional protection at times when hormonal contraceptive doses might be missed. Female subjects may be included without a negative urine pregnancy test if they are surgically sterile or at least 2 years post-menopausal. Male subjects and their female sexual partners should use an acceptable method of birth control (as noted above) during the study.

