#### 9.1.3 HANDLING OF MISSING VALUES

Unless otherwise stated, missing values will be imputed via the LOCF method.

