#### **9.2** SECONDARY EFFICACY OUTCOMES

The secondary objectives of the study are to assess the effect of AXS-05 versus bupropion on (based on mITT population unless otherwise stated):

- Change from baseline in QIDS-SR-16 (Quick Inventory of Depressive Symptomatology-Self-Rated);
- 2. CGI-I (Clinical Global Impressions-Improvement);
- 3. Change from baseline in CGI-S (Clinical Global Impressions-Severity);

AXSOME Therapeutics, Inc.	CONFIDENTIAL	Version 1.0—11 December 2018
AXS-05-MDD-201 SAP	Page 11 of 16	

- 4.
- 5. Percentage of responders on MADRS (response defined as  $\geq$  50% reduction from baseline)
- 6. Percentage of responders on MADRS (response defined as  $\geq$  30% reduction from baseline)
- 7. Percentage achieving remission on MADRS (remission defined as MADRS  $\leq 10$ )
- 8. Percentage achieving remission on MADRS (remission defined as MADRS  $\leq 12$ )
- 9. Overall treatment effects on change from baseline in MADRS (weeks 1-2, weeks 1-3, weeks 1-4, weeks 4-6)
- 10. Change from baseline on item 1 (apparent sadness) of MADRS
- 11. Change from baseline in MADRS-6 (MADRS 6-item subscale)
- Overall treatment effects on change from baseline in MADRS-6 (weeks 1-2, weeks 1-3, weeks 1-4, weeks 4-6)
- 13. Percentage of responders on MADRS-6 (response defined as  $\geq$  50% reduction from baseline)
- 14. Percentage of responders on MADRS-6 (response defined as  $\geq$  30% reduction from baseline)
- 15. Overall treatment effects on change from baseline in QIDS-SR-16 (weeks 1-2, weeks 1-3, weeks 1-4, weeks 4-6)
- 16. Percentage of responders on QIDS-SR-16 (response defined as  $\geq$  50% reduction from baseline)
- 17. Percentage of responders on QIDS-SR-16 (response defined as  $\geq$  30% reduction from baseline)
- 18. Percentage achieving remission on QIDS-SR-16 (remission defined as QIDS-SR-16  $\leq$  6)
- 19. Percentage achieving remission on QIDS-SR-16 (remission defined as QIDS-SR-16  $\leq$  5)
- 20. Overall treatment effects on change from baseline in (week 1, weeks 1-2, weeks 1-3, weeks 1-4, weeks 4-6)
- 21. Percentage of responders on (response defined as  $\geq$  50% reduction from baseline)
- 22. Percentage of responders on (response defined as  $\geq$  30% reduction from baseline)
- 23. Time to clinically meaningful improvement on MADRS (reduction from baseline of ≥ 2); QIDS-SR-16 (reduction from baseline of ≥ 10%, ≥ 20%);
  MADRS-6 (reduction from baseline of ≥ 10%, ≥ 20%)

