- 24. Time to clinical improvement based on the CGI-I (score of 3 [minimally improved] or less)
- 25. Treatment effects in patients with severe depression based on MADRS (defined as MADRS  $\geq$  30,  $\geq$  35); severe or very severe depression based on QIDS-SR-16 (defined as QIDS-SR-16  $\geq$  16)
- 26. Treatment effects based on MADRS in patients who had ≥1 prior antidepressant treatments during the current major depressive episode
- 27.

   28.

Efficacy variables related to change from baseline will be analyzed via the methods outlined in the analysis for the primary efficacy variable.

AXSOME Therapeutics, Inc. AXS-05-MDD-201 SAP **CONFIDENTIAL** Page 12 of 16 CGI-I (Clinical Global Impression Scale-Improvement) is a 7-point scale (1= Very Much Improved and 7= Very Much Worse), and will be analyzed using Cochran-Mantel-Haenszel test using score=ridit option. Frequency of the categories will also be presented.

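### The primary MMRM fixes one variance for all five weeks; if the SD of MADRS change rises over time, Week 1 intervals are too wide and Week 6 intervals too narrow

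*SAP*

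**What the plan says.** SAP 9.1.2 analyses change from baseline in MADRS with treatment, week (five levels), treatment-by-week, "baseline value as a covariate, and subject as a random effect". On covariance it says: "SAS default covariance structure (variance components) will be assumed". On estimation: "The MMRM with maximum likelihood estimation will utilize the following pseudo- SAS code for analysis". The code itself does not appear in the available text, so the degrees-of-freedom method and any REPEATED statement cannot be read.

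The primary test is the overall treatment effect. In addition, "for completeness treatment difference at each post baseline week will also be presented", with two-sided 95% confidence intervals. SAP 9.2 (item 9) adds MADRS effects over weeks 1-2, 1-3, 1-4 and 4-6, and items 12 and 15 do the same for MADRS-6 and QIDS-SR-16. The model also carries over to the secondaries: "Efficacy variables related to change from baseline will be analyzed via the methods outlined in the analysis for the primary efficacy variable". On gaps, SAP 9.1.3 says: "Unless otherwise stated, missing values will be imputed via the LOCF method". SAP 9.4 makes no multiplicity adjustment.

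**The concern.** A random subject effect plus a single residual variance is compound symmetry: the same total variance at every visit and the same correlation between every pair of visits. The SAP offers no reason for this, no heterogeneous alternative, no robust standard error and no sensitivity structure.

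A rising SD is plausible. Everyone enters with MADRS of at least 25 at both Screening and Baseline (Protocol 7.2.1), and patients can then diverge over six weeks. If that happens, one pooled variance overstates the uncertainty at Week 1 and understates it at Week 6. Those are the results a reader consults for onset and for end-of-treatment effect.

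A separate, smaller matter is that ML divides the between-subject sum of squares by the number of subjects without allowing for estimated parameters. That makes the primary test slightly anti-conservative whatever the SD pattern.

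**Working it through.** **Inputs from the documents.** About 60 subjects, 30 per arm (SAP 9.5); five post-baseline weeks (SAP 9.1.2); two-sided 0.05 (SAP 6.0). There is no SD, correlation, effect size or power figure to reproduce.

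**Assumptions.** Four SD patterns for Weeks 1, 2, 3, 4 and 6; correlation either 0.6 between all visits or 0.85 per week of separation; reference degrees of freedom from 57 (subject level: 60 minus intercept, treatment and baseline) to 232 (residual).

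**Step 1: what the model estimates.** With complete vectors, ML gives λ = SSB/60 between subjects and σe² = SSW/(60×4) within. The fitted variance at every week is (λ + 4σe²)/5, which estimates the plain average of the five weekly variances.

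| Assumed SDs | Mean variance | Pooled SD | Pooled / Week 1 SD | Pooled / Week 6 SD |
|---|---|---|---|---|
| 7.5, 8, 8, 8.3, 8.5 | 325.39/5 = 65.08 | 8.07 | 1.08 | 0.95 |
| 6, 7, 8, 8.5, 9 | 302.25/5 = 60.45 | 7.77 | 1.30 | 0.86 |
| 5, 6.5, 7.5, 8.5, 10 | 295.75/5 = 59.15 | 7.69 | 1.54 | 0.77 |

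**Step 2: ML and degrees of freedom.** With equal SDs and correlation 0.6, ML shrinks the variance by (3.4×57/60 + 1.6×232/240)/5 = 0.955, a factor of 0.977 on the SE. Using 232 instead of 57 degrees of freedom multiplies the critical value by 1.970/2.002 = 0.984. Together these give 0.962, so a corrected interval is about 1/0.962 = 1.04 times as wide. Multiplying the ratios in Step 1 by about 0.96 gives the simulated widths relative to an unstructured model to within about one percentage point.

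**Step 3: simulated null rejection at nominal 5%** (40,000 trials per scenario; ranges cover both correlation patterns and both degrees of freedom).

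| SD pattern | Week 1 | Week 6 | Week 1 CI width | Week 6 CI width |
|---|---|---|---|---|
| Equal, 8 | 5.2-5.9% | 5.2-5.9% | about -4% | about -4% |
| 7.5 to 8.5 | 3.7-4.1% | 6.6-7.0% | +4% | -8% |
| 6 to 9 | 1.3-1.5% | 9.2-9.9% | +25% | -17% |
| 5 to 10 | 0.3-0.4% | 13.3-14.0% | +48% | -26% |

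REML alone (57 df) leaves Week 6 at 8.5-12.6% under the two steeper rises. REML with unstructured covariance gives 4.6-5.3% for every week, window and overall test in all scenarios (57 df standing in for Kenward-Roger).

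**Step 4: a second simulation with different assumptions** (SDs rising linearly, 20,000 trials, correlation 0.6 throughout or 0.8 per week). Coverage of nominal 95% intervals at Week 1 and Week 6 was 0.967 and about 0.906 (SD 7 to 9), 0.986 and 0.870 (6 to 10), and 0.997 and 0.832 (5 to 11). Week-specific variances gave 0.948-0.952 throughout.

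**Step 5: the primary overall test.** It uses subject means, so the weekly SD pattern drops out. The ML divisor gives 2·P(t57 > 2.002·√(57/60)) = 0.0559 with 57 df and 2·P(t57 > 1.970·√(57/60)) = 0.0598 with 232 df. REML with 57 df brings it to 4.8-5.1%.

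**Step 6: part-period windows.** Taken as contrasts from the full model under the two steeper rises, weeks 1-2 reject at 1.2-3.4%, weeks 1-3 at 2.3-4.9% and weeks 4-6 at 8.8-11.9%. Refitted to their own weeks, they reject at 5.2-6.1% in every scenario. With equal SDs and decaying correlation, full-model windows from weeks 1-2 to 1-4 give 6.6-7.3%; that comes from the common-correlation assumption, not the common variance.

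**Step 7: LOCF.** With 20% random dropout carried forward (correlation 0.85 per week), Week 1 and Week 6 rejection was 4.0-4.3% and 6.4-6.9%, 1.5-1.7% and 9.2-9.7%, and 0.4% and 12.6-13.2% for the three rises. The pattern is unchanged.

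**The case against.** The affected outputs are subordinate: the overall effect is primary, weekly differences are supplementary, and this is a small Phase 2 study with no multiplicity control. That stands, and it limits the point to an improvement.

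The size depends on SDs the documents do not give. The entry threshold restricts baseline spread, baseline is already a covariate, and MADRS has a floor at zero, so a strong response could flatten or reverse the rise. The steepest scenario needs the SD to double. This also stands, and the mild case should carry most weight. There Week 6 rejection is 6.6-7.0%, of which part is the ML and df effect: with REML and 57 df it is about 6.2%.

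The code is not visible and might differ from the prose. However, either reading that fits the prose still gives one variance for all weeks. If variance components described a REPEATED statement with no random subject effect, the overall test itself would reject at about 28-30%. The stated random effect argues against that reading, but it is a further reason to check the code.

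Windows may be refits, in which case they are sound. The SAP does not say.

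LOCF cannot fill a missing Week 1 unless baseline is carried forward, so the complete-data formulas are approximate. This does not change the result. The simulations covered neither Kenward-Roger itself nor the individual secondary scales.

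**Conclusion.** The point holds as a conditional statement. The SAP text forces one variance on five weeks. If the SD of MADRS change rises, Week 1 precision is understated and Week 6 precision overstated. Under assumed rises from mild to a doubling, Week 6 rejection runs from 6.6% to 14.0% and Week 1 from 4.1% down to 0.3%. With equal SDs there is no material problem. The primary overall test is at 5.6-6.0% in all scenarios, a small ML and degrees-of-freedom effect unrelated to the common variance. The primary conclusion is therefore little affected. What is at risk is the reading of onset and end-of-treatment results, and of any change-from-baseline secondary whose spread changes over time. The direction follows from the model; the size rests on assumed SDs and correlations.

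**What to change.** In SAP 9.1.2, replace the covariance and estimation sentences with: REML; unstructured within-subject covariance across the five visits; no separate random subject effect; Kenward-Roger degrees of freedom; and a pre-stated fallback order if the fit does not converge, for example heterogeneous Toeplitz, then heterogeneous AR(1). Apply the same model to all change-from-baseline secondaries in SAP 9.2. State whether the part-period effects are contrasts from the full five-week model or refits to the named weeks. If the SAS code in the full SAP differs from the prose, reconcile the two.

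The cost is SAP wording and one model statement, 15 covariance parameters estimated from about 60 subjects, and a small loss of degrees of freedom. If the SDs turn out equal, intervals are about 4% wider, which is roughly what correcting the ML divisor and the degrees of freedom would produce anyway. The revision should be final before database lock and unblinding, as SAP 3.0 requires.

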#### 9.1.3 HANDLING OF MISSING VALUES

Unless otherwise stated, missing values will be imputed via the LOCF method.

#### **9.2** SECONDARY EFFICACY OUTCOMES

The secondary objectives of the study are to assess the effect of AXS-05 versus bupropion on (based on mITT population unless otherwise stated):

- Change from baseline in QIDS-SR-16 (Quick Inventory of Depressive Symptomatology-Self-Rated);
- 2. CGI-I (Clinical Global Impressions-Improvement);
- 3. Change from baseline in CGI-S (Clinical Global Impressions-Severity);

AXSOME Therapeutics, Inc.	CONFIDENTIAL	Version 1.0—11 December 2018
AXS-05-MDD-201 SAP	Page 11 of 16	

- 4.
- 5. Percentage of responders on MADRS (response defined as  $\geq$  50% reduction from baseline)
- 6. Percentage of responders on MADRS (response defined as  $\geq$  30% reduction from baseline)
- 7. Percentage achieving remission on MADRS (remission defined as MADRS  $\leq 10$ )
- 8. Percentage achieving remission on MADRS (remission defined as MADRS  $\leq 12$ )
- 9. Overall treatment effects on change from baseline in MADRS (weeks 1-2, weeks 1-3, weeks 1-4, weeks 4-6)
- 10. Change from baseline on item 1 (apparent sadness) of MADRS
- 11. Change from baseline in MADRS-6 (MADRS 6-item subscale)
- Overall treatment effects on change from baseline in MADRS-6 (weeks 1-2, weeks 1-3, weeks 1-4, weeks 4-6)
- 13. Percentage of responders on MADRS-6 (response defined as  $\geq$  50% reduction from baseline)
- 14. Percentage of responders on MADRS-6 (response defined as  $\geq$  30% reduction from baseline)
- 15. Overall treatment effects on change from baseline in QIDS-SR-16 (weeks 1-2, weeks 1-3, weeks 1-4, weeks 4-6)
- 16. Percentage of responders on QIDS-SR-16 (response defined as  $\geq$  50% reduction from baseline)
- 17. Percentage of responders on QIDS-SR-16 (response defined as  $\geq$  30% reduction from baseline)
- 18. Percentage achieving remission on QIDS-SR-16 (remission defined as QIDS-SR-16  $\leq$  6)
- 19. Percentage achieving remission on QIDS-SR-16 (remission defined as QIDS-SR-16  $\leq$  5)
- 20. Overall treatment effects on change from baseline in (week 1, weeks 1-2, weeks 1-3, weeks 1-4, weeks 4-6)
- 21. Percentage of responders on (response defined as  $\geq$  50% reduction from baseline)
- 22. Percentage of responders on (response defined as  $\geq$  30% reduction from baseline)
- 23. Time to clinically meaningful improvement on MADRS (reduction from baseline of ≥ 2); QIDS-SR-16 (reduction from baseline of ≥ 10%, ≥ 20%);
  MADRS-6 (reduction from baseline of ≥ 10%, ≥ 20%)
- 24. Time to clinical improvement based on the CGI-I (score of 3 [minimally improved] or less)
- 25. Treatment effects in patients with severe depression based on MADRS (defined as MADRS  $\geq$  30,  $\geq$  35); severe or very severe depression based on QIDS-SR-16 (defined as QIDS-SR-16  $\geq$  16)
- 26. Treatment effects based on MADRS in patients who had ≥1 prior antidepressant treatments during the current major depressive episode
- 27.

   28.

Efficacy variables related to change from baseline will be analyzed via the methods outlined in the analysis for the primary efficacy variable.

AXSOME Therapeutics, Inc. AXS-05-MDD-201 SAP **CONFIDENTIAL** Page 12 of 16 CGI-I (Clinical Global Impression Scale-Improvement) is a 7-point scale (1= Very Much Improved and 7= Very Much Worse), and will be analyzed using Cochran-Mantel-Haenszel test using score=ridit option. Frequency of the categories will also be presented.

#### 9.3 INTERIM ANALYSES

No interim analysis is planned.

#### 9.4 ADJUSTMENTS FOR MULTIPLICITY

As this study is a Phase 2 study with a small sample size no p-value adjustments will be made.

## 9.5 POWER AND SAMPLE SIZE JUSTIFICATION

Approximately 60 subjects (30 per arm) whose diagnosis of MDD with a current major depressive episode of moderate or greater severity is confirmed by an independent assessor based on clinical review will be included in the analyses. The sample size was determined based on prior reported experience with trials of a similar stage, in a similar patient population, with a similar objective.

A sufficient number of subjects will be screened to achieve the planned number of subjects.

# **10.0** SUMMARIES OF MEASURES OF SAFETY

Safety analyses will be performed for the safety population. Safety evaluations will be based on the incidence, severity, relatedness, and type of adverse events, as well as on clinically significant changes in the subject's physical examination, vital signs, and clinical laboratory results. Safety variables will be tabulated and presented by study drug actually received.

Because there is no pre-specified safety outcome defined in terms of AEs, clinically relevant laboratory parameters, or vital signs, any formal comparisons between the treatment arms with respect to specific safety parameters will be post-hoc.

C-SSRS (Columbia - Suicide Severity Rating Scale) will be summarized as a safety assessment.

## **10.1** EXTENT OF EXPOSURE

Summary statistics of exposure to study drug will be tabulated by treatment group, and by duration.

#### **10.2** ADVERSE EVENTS

Each AE and SAE term recorded on the case report forms (CRFs) by primary system organ class (SOC) will be mapped to a preferred term using the MedDRA dictionary. The investigator will assess AE severity and relationship to the study treatment.

A treatment emergent adverse event (TEAE) is defined as any AE with an onset date on or after date of randomization, or any ongoing event on the date of first dose that worsens in severity after date of randomization. Only non-serious TEAEs with an onset date prior to date of last dose and serious TEAEs

AXSOME Therapeutics, Inc. AXS-05-MDD-201 SAP CONFIDENTIAL Page 13 of 16 Version 1.0—11 December 2018

with an onset date prior to date of the final visit + 30 days will be tabulated in summary tables. However, all AEs recorded will be listed. For the purpose calculating treatment emergence and inclusion in summary tables, incomplete onset dates will be imputed as detailed in Appendix A.

AEs will be summarized by the number and percent of subjects in each primary SOC and preferred term. Patients will be counted only once for each primary SOC and each preferred term. Summary tables of AEs by primary SOC, preferred term and severity will be provided. If a subject has more than one AE coded to the same preferred term, the subject will be counted only once for that preferred term by using the event with the highest severity. Similarly, if a subject has more than one AE within a primary SOC category, the subject will be counted only once in that SOC category by using the event with the highest severity. AEs by primary SOC, preferred term and relationship to study drug will be provided as well. If a subject has more than one AE coded to the same preferred term, the subject will be counted only once for that preferred term by using the most related event. Similarly, if a subject has more than one AE within a primary SOC category, the subject will be counted only once in that primary SOC category by using the most related event. Similarly, if a subject has more than one AE within a primary SOC category, the subject will be counted only once in that primary SOC category by using the most related event. Similarly, if a subject has more than one AE within a primary SOC category, the subject will be counted only once in that primary SOC category by using the most related event. In addition, serious adverse events (SAE) by primary SOC and preferred term will be provided. Deaths and SAEs will be summarized similarly to AEs. All adverse event tables will also include the total number of events, counting multiple events per patient.

In the AE summary, preferred terms within each SOC will appear in alphabetical order as well as in decreasing order of total incidence.

Frequencies for deaths and hospitalizations will also be summarized by treatment group and overall.

Other safety analyses will be performed as appropriate

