9.1.2 Visit 2, Baseline (Day 0)

Subjects will return for Visit 2 up to 28 days after Visit 1. The interval may be extended, if necessary and after discussion with the Axsome Medical Monitor, to accommodate medication washout or repeat screening procedures. The following procedures will be performed at Baseline (Day 0):

- Review and confirm inclusion/exclusion criteria.
- Record vital signs, including: Blood pressure, pulse, respiratory rate, and oral temperature after subject has been seated for 5 minutes.
- Review and record AEs since last visit.
- Review and record any current concomitant medication use (including OTC, vitamins, and supplements).
- Collect urine sample for on-site drug screening and urine pregnancy test (if female).
- •
- Administer evaluations:
 - MADRS (≥ 25 inclusive)
 - \circ CGI-S (\geq 4 inclusive)
 - o QIDS-SR-16
 - C-SSRS (since last visit)
- Randomize subject once it is determined that subject satisfies all of the inclusion and exclusion criteria (on the basis of the screening and baseline assessments described above). Eligible subjects will be randomized sequentially and assigned the corresponding kit number.
- Dispense 1 study drug bottle from the subject assigned kit.
- Instruct subject to begin to dose 1 tablet the following morning for the next three days, on an empty stomach (at least 2 hours pre- or 2 hours post-prandial), orally with water.
- Schedule Visit 3 telephone call for Day 3.
- •

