10.1.5 Treatment-Emergent Adverse Events

An AE is defined as treatment emergent if the first onset or worsening is after the first administration of the study drug and not more than 30 days after the last study visit.

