12.4.3.1 Adverse Events

Adverse events will be coded by system organ class (SOC) and preferred term using the Medical Dictionary for Regulatory Activities reporting system. Treatment-emergent AEs are defined as any of the following:

- Non-serious AEs with onset on the date of first dose of treatment with the study drug through follow up (7 days after the last dose of study drug);
- Serious AEs with onset on the date of first dose of treatment with the study drug through 30 days after the last dose of study drug;

The number and percentage of subjects with TEAEs will be displayed for each treatment group by SOC and preferred term. Additionally, TEAEs will be tabulated for each treatment group by severity and by relationship to the study drug. A listing of SAEs will be provided if applicable.

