17.2 Schedule of Assessments

Visit	Screening Visit 1	Baseline Visit 2	Phone Call Visit 3	Visit 4	Visit 5	Visit 6	Visit 7	Visit 8 / ET	Visit 9 Follow-up ^a
Study Day	-28 to -1	0	3 (+1)	7 (±2)	14 (±2)	21 (±2)	28 (±2)	42 (±2)	49 (±2)
Week	-4 to -1			Week 1	Week 2	Week 3	Week 4	Week 6	Week 7
Informed Consent	X ^b								
Inclusion/Exclusion Criteria	Х	Х							
Demographics	Х								
Medical/Psychiatric History	Х								
Medication History	Х								
Physical Examination	Х							Х	
Vital Signs, Height/Weight ^c	Х	Х		Х	Х	Х	Х	Х	
Laboratory Tests ^d	Х							Х	
Urine Drug Screen ^e	Х	Х						Х	
Serum Ethanol ^e	Х							Х	
Urine Pregnancy Test (all female subjects)	Х	Х						Х	
SCID-5-CT	Х								
MADRS	Х	Х		Х	Х	Х	Х	Х	
QIDS-SR-16	Х	Х		Х	Х	Х	Х	Х	
CGI-S (Severity)	Х	Х		Х	Х	Х	Х	Х	
CGI-I (Improvement)				Х	Х	Х	Х	Х	
C-SSRS	Х	Х		Х	Х	Х	Х	Х	Х
Randomization		Х							
Instruct to begin BID dosing			Х						
Study Drug Dispensation ^h		Х		Х	Х	Х	Х		
Study Drug Accountability			Х	Х	Х	Х	Х	Х	
Prior and Concomitant Medications	Х	Х	Х	Х	Х	Х	Х	Х	Х
Adverse Events	Х	Х	Х	Х	Х	Х	Х	Х	Х

Abbreviations: SCID-5-CT = Structured Clinical Interview for Diagnostic and Statistical Manual of Mental Disorders, Fifth Edition, Clinical Trials Version; ET = early termination; EOS = End of Study; MADRS = Montgomery-Åsberg Depression Rating Scale; QIDS-SR-16 = Quick Inventory of Depressive Symptomatology-Self- Rated; CGI-I = Clinical Global Impressions–Improvement; CGI-S = Clinical Global Impressions–Severity; C-SSRS = Columbia - Suicide Severity Rating Scale;

a Safety follow-up visit to be performed telephonically.

b Informed consent must be signed prior to any study procedures being performed.

c Vital signs, including blood pressure, heart rate, respiratory rate, and oral body temperature, will be measured after the subject has been in a seated position for at least 5 minutes. Height will be measured at Visit 1 and weight at Visit 1 and Visit 8 (EOS or ET).

d Clinical laboratory tests will include hematology, serum chemistry, urinalysis and thyroid panel.

e May be performed at other study visits per investigator judgment. Subjects with positive urine drug screen or serum ethanol levels at Visit 1 may be allowed in study depending on circumstances described to the Medical Monitor and a negative repeat UDS is obtained before Visit 2.

f

h Subjects will begin to take study drug the morning of Day 1 (morning after Visit 2).

APPENDICES

- B. Regulations and Good Clinical Practice Guidelines

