#### **For Adverse Events**

If onset date is completely missing, onset date is set to date of randomization.

If (year is present and month and day are missing) or (year and day are present and month is missing):

- If year = year of randomization, then set month and day to month and day of randomization
- If year < year of randomization, then set month and day to December 31.
- If year > year of randomization, then set month and day to January 1.

If month and year are present and day is missing:

- If year=year of randomization and
  - If month = month of randomization then set day to day of first dose
  - If month < month of first dose then set day to last day of month
  - If month > month of first dose then set day to first day of month
- If year < year of randomization then set day to last day of month
- If year > year of randomization then set day to first day of month

For all other cases, set onset date to date of randomization.

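### SAP 10.2 starts the onset limb of the TEAE definition at randomization (Day 0), one day before the first tablet, so adverse events that begin on a drug-free day are tabulated as treatment-emergent

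*SAP*

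**What the plan says.** **SAP 10.2** has two limbs. The onset limb reads: "A treatment emergent adverse event (TEAE) is defined as any AE with an onset date on or after date of randomization". The worsening limb adds "any ongoing event on the date of first dose that worsens in severity after date of randomization". The sentence that follows limits what enters the summary tables, but only at the upper end: before last dose for non-serious events, and before the final visit plus 30 days for serious ones.

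**Protocol 9.1.2** places randomization at Visit 2, Day 0: "Randomize subject once it is determined that subject satisfies all of the inclusion and exclusion criteria". The same list of procedures fixes the start of dosing: "Instruct subject to begin to dose 1 tablet the following morning for the next three days". Footnote h of the Schedule of Assessments (protocol 17.2) confirms that this is the morning of Day 1.

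**Protocol 10.1.5**: "An AE is defined as treatment emergent if the first onset or worsening is after the first administration of the study drug".

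**Protocol 12.4.3.1** counts "Non-serious AEs with onset on the date of first dose of treatment with the study drug", and uses the same starting date for serious events.

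**SAP Appendix A**, adverse event rules: "If onset date is completely missing, onset date is set to date of randomization". Other rules in the same list set or compare the onset date against the day or month of first dose.

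**The concern.** Day 0 is a drug-free day by design for every subject who follows the schedule. Because the onset limb works on dates alone, it takes in every event that begins on that day, including one that began before the randomization step. If a subject starts drug late, the extra pre-dose days count as well.

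The SAP does not mention or justify a departure from the protocol's starting point. Safety and tolerability is the only objective in protocol section 5, and TEAE incidence is a listed safety endpoint in 12.1.1. An event that study drug cannot have caused would still appear in the tables by system organ class, preferred term, severity and relationship.

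The SAP is also inconsistent with itself. Section 8.0 classifies medications by first administration. A remedy started and stopped on Day 0 would be a prior medication, while the event it treated would be a TEAE.

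**Working it through.** The plan gives no figure to reproduce. The check is to trace the dates, count the days, and give an illustrative range.

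**1. Does anything else remove Day 0 events?**
- Collection: protocol 10.2 collects adverse events from consent, so Day 0 events are in the database.
- Table filter: SAP 10.2 sets upper limits only.
- Safety population: SAP 5.2 drops undosed subjects but keeps all events of a dosed subject.

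Nothing removes them.

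**2. Onset days for non-serious events, subject on schedule** (randomized Day 0, first dose Day 1, last dose Day 42)
- SAP rule: Day 0 to Day 41 = 42 days, of which 1 is before any dose. 1/42 = 2.4%.
- Start moved to first dose: Day 1 to Day 41 = 41 days, none on a calendar day before first dose.

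**3. Worsening limb.** It requires worsening after the date of randomization. After Day 0 means Day 1 or later, so on schedule this limb admits no drug-free day. Its fault is that it uses both anchors in one clause: ongoing at first dose, worse since randomization.

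**4. Appendix A.** Take a subject randomized on 31 August with first dose on 1 September of the same year.
- Onset in August, day missing. The month equals the month of randomization, so the day becomes the day of first dose, giving 1 August, 30 days before randomization. The month is also earlier than the month of first dose, so the next rule gives 31 August. Under SAP 10.2 the first result is not a TEAE and the second is.
- Onset in September, day missing. None of the three month rules applies, so the event falls to the residual rule and is set to 31 August, against its recorded month.

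With first dose as the only anchor, the August event goes to 31 August (pre-treatment) and the September event to 1 September (treatment-emergent).

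**5. Illustrative size.** The documents give no adverse event rate. Let p be the share of subjects with an onset on Day 0 and take the planned 60 subjects. Expected number = 60p. Chance of at least one = 1 − (1 − p)^60, treating subjects as independent.

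| p (assumed) | Expected of 60 | Expected per arm of 30 | Chance of at least one |
|---|---|---|---|
| 0.5% | 0.3 | 0.15 | 26% |
| 1% | 0.6 | 0.3 | 45% |
| 2% | 1.2 | 0.6 | 70% |

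The 60 are compliant completers, so the safety population may be larger. The expected counts scale in proportion.

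**The case against.** The case for leaving the rule alone has some force.

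- **No bias between arms.** Day 0 precedes exposure in both randomized, blinded arms, so the expected difference is zero. Protocol 12.4.3 plans no formal safety comparisons. This stands.
- **The rule over-includes.** Its start loses no on-drug event, all adverse events are listed, and protocol 10.2.3 records start date and time, so Day 0 events can be found. Timing is one of the criteria for relatedness in protocol 10.2.2.5, which should limit distortion of the relationship table. This also stands, but it does not make a known pre-dose event informative about the drug. The useful caution, defaulting missing dates to treatment-emergent, can be kept without it.
- **The protocol is date-based too.** Section 12.4.3.1 would admit an event early on Day 1, before the tablet. That is true, but it concerns part of one day and not a whole drug-free day.

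Three stronger readings are tempting, and the documents do not support them.

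- A reader might infer that the worsening limb also lets in a drug-free day. On schedule it does not (step 3).
- A reader might infer that Day 0 is an especially likely day for events because psychotropics are withdrawn before Visit 2. Exclusion criterion 13 requires at least 1 week or 5 half-lives, whichever is longer, since the last prohibited dose. Events that began during washout have an onset before Day 0, outside the onset limb.
- A reader might infer a shift of 3.3 percentage points in an arm. That is 1/30, the weight of one whole subject in one arm, and applies only if that subject has no other TEAE in the same row. The expected shift under the assumed range is 0.15/30 to 0.6/30, or 0.5 to 2 points at most, in each arm alike.

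**Conclusion.** The point holds for the onset limb. SAP 10.2 labels adverse events that begin on Day 0 as treatment-emergent, although no drug has been taken and both protocol definitions start at first dose. The worsening limb and Appendix A are at fault for mixing two anchors; the worsening limb adds no drug-free day on schedule.

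The effect is small: 1 of 42 eligible non-serious onset days (2.4%) for a subject on schedule, and about 0.3 to 1.2 of 60 subjects if 0.5% to 2% have a Day 0 onset. That range is an assumption. The share would be larger for a late starter, but the documents give no figure for late starts. The cost is misattribution and noise in the TEAE tables. No bias between arms is shown or expected. The rule is worth correcting because it departs from the protocol without explanation on its main safety endpoint and is easy to put right.

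**What to change.** Make these changes in one SAP revision.

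1. **SAP 10.2.** Define a TEAE as an adverse event with onset on or after the date of first dose of study drug, or an event ongoing at first dose that worsens on or after that date. The words *on or after* are needed in the worsening limb. Substituting first dose for randomization in the present wording would read *after date of first dose* and would drop genuine worsening on Day 1. Where recorded times allow, use them to separate events before and after the first tablet on Day 1.
2. **Appendix A, adverse event rules.** Use the first-dose date as the only anchor throughout. This must accompany item 1. If only 10.2 changed, a completely missing onset date would still be set to Day 0, and the event would fall out of the TEAE tables.
3. **Listings.** Keep Day 0 events and mark them as pre-treatment.

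The cost is SAP wording and one date variable in programming. The first-dose date is already needed for SAP 8.0, the worsening limb and Appendix A. Data collection does not change.

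The end of the TEAE window also differs between the SAP and the two protocol definitions. That is a separate matter, but it can be reconciled in the same edit.
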